13.0 Risks to Participants

13.1 Foreseeable Risks:

- Distress or fatigue associated with clinical questionnaires, performance measures, interviews, or intervention performed as part of participation in the study: Questionnaires, performance measures, interviews, and intervention will be delivered by research assistants trained and supervised by the PI, an occupational therapist with more than 10 years of experience working with the stroke population. Participants who experience distress, embarrassment, or fatigue will be able to take breaks during testing and intervention session. If needed, testing may be completed in multiple short sessions.
- Discomfort or mild skin irritation associated with the activPAL activity monitoring protocol: The adhesive used to adhere the ActivPAL monitor to the participant's thigh is a common adhesive used in the healthcare setting. Participants who have a history of skin irritation are excluded from the study. Participants will receive instructions to monitor their skin for signs of irritation. If skin irritation occurs during the study, the participant will be instructed to transfer the activPAL to the opposite leg and continue to monitor for signs of irritation. Should irritation persist, participants will be instructed to remove the device and alternative strategies for activity monitoring will be explored (e.g., alternative wearing).

NCT05029284

VERSION DATE: 07.21.2023

schedules, use of non-adhesive strategies for maintaining device position).

- Risk for injury (such as a fall-related injury) while engaging in daily activities planned during intervention processes:
 Intervention processes will be supervised by the PI, a licensed occupational therapist with more than 10 years of experience in stroke rehabilitation. While planning activities, participants will be directly prompted to identify possible safety concerns and develop plans to assure safety (e.g. involve support person). Activities planned during intervention are daily activities that stroke survivors encounter in daily life outside of intervention. As such, engaging in these activities pose minimal risk. In addition, during activity planning, the study interventionist will also follow a safety protocol that clarifies whether the presence of a support person is required when completing the participant's chosen activity (see Appendix A). In the event of an injury associated with intervention, participants will be instructed to seek appropriate medical care.
- Identification of severe depressive symptoms. During the assessments, we will use the Neuro-QOL Depression Short Form to measure depressive symptoms. This is a validated measure of depressive symptom load among people with stroke [62]. A raw score of ≥26 on this measure indicates that the participant is experiencing severe depressive symptoms. If the participant meets or exceeds this score of 26 on this measure, the study team will verbally discuss the results with the participant, provide the participant with a packet (via electronic mail) which contains mental health crisis support information and an education sheet on mental health after stroke published by the American Congress of Rehabilitation Medicine, and encourage the participant to discuss these symptoms with their primary care physician
- Inconvenience caused by study visits and telephone calls: Study
 visits and telephone calls will be scheduled according to the
 participants' preferences, including options for evening and
 weekend visits. We will also minimize inconvenience by using
 individual participants' preferred forms of contact for scheduling
 and session reminders (e.g. telephone call, email, text messaging).
- The potential for breach of confidentiality: All identifiable
 information will be stored separate from the participant's research
 data. Each participant will be assigned a unique study ID number.
 Electronic data will be stored in an encrypted and passwordprotected database (REDCap) and in the UMN University Box
 Secure Storage.

NCT05029284

VERSION DATE: 07.21.2023

13.2 Reproduction Risks: Not applicable

13.3 Risks to Others: Not applicable

14.0 Potential Benefits to Participants

14.1 Potential Benefits: There is potential that participants may derive benefit from participation in the teleABLE intervention, however there is no guarantee. Participants may experience improvements in sedentary behavior and health-related quality of life.

15.0 Statistical Considerations

- 15.1 Data Analysis Plan: The purpose of this formative research is to refine our research and intervention protocol based on (1) qualitative analyses of stakeholder data and (2) descriptive analyses of process data.
 - (1) **Stakeholder data:** Audiorecorded interviews will be transcribed and interview transcripts, intervention session notes, and therapist reflective logs will be read by two researchers who will identify codes and, subsequently, themes that guide research protocol refinement and intervention protocol refinement. Discrepancies will be resolved through discussion with a third researcher.
 - (2) **Process data:** Audiorecorded intervention sessions will be rated against the teleABLE Intervention Checklist by an independent assessor to indicate the presence or absence of the intervention components in each session. Study documentation related to attendance (sessions/week) and safety (adverse event count), and participant rating of satisfaction (Client Satisfaction Questionnaire-8) will also be computed. Descriptive process data will be compared against pre-established benchmarks.
- 15.2 Power Analysis: Because the focus of this research is to refine our research and intervention protocol, the sample size was selected based on the data required to inform these protocols rather than tests of statistical significance. All volunteers will complete assessments at 2 time points, 12 intervention sessions, and 2 interviews. Once data are collected from 5 volunteers (60 intervention sessions, 10 interviews), thematic analyses will be initiated. Additional volunteers will be recruited as needed to achieve thematic saturation. We anticipate achieving thematic saturation with 5-10 participants (60-120 intervention sessions, 10-20 interviews).
- 15.3 Statistical Analysis: Descriptive sample statistics will be computed to describe (1) presence of intervention components in each session, (2) number of sessions attended/week, (3) adverse event count, and (4) satisfaction [Client Satisfaction Questionnaire-8]. These scores will be compared against pre-established benchmarks for (1) intervention components present in ≥90% of sessions, (2) 1.5

Page 28 of 44

Template Revised On: 10/28/2022

VERSION DATE: 07.21.2023

to 2.5 sessions attended/week, (3) \leq 1 adverse event, and (4) mean Client Satisfaction Questionnaire-8 score \geq 3.

15.4 Data Integrity: Data will be collected and monitored using strategies to assure data integrity.

Data collection: Questionnaire-based data and interviews will be collected over synchronous videoconferencing where the volunteer provides verbal response and the assessor directly enters the response into REDCap (questionnaires) or audiorecords (interviews). At the end of the assessment or interview session, the assessor will complete a checklist to confirm that all questionnaires and interviews were completed, and that the interview was uploaded to the appropriate secure folder. Reasons for missing data will be documented. Instructions for activPAL monitoring will also be provided during the assessment session, and the assessor will follow up with the participant via telephone within 48 hours to confirm that the monitor was donned appropriately. Intervention documentation will be entered by the treating therapist in REDCap as soon as possible following session completion, with the expectation that session documentation will be completed within 48 hours.

Data monitoring: The PI will meet with the study team on a weekly basis to review the status of the study. This will include reviewing the results of (1) chart audits of study records of completed volunteers to assure completeness of data and contemporary documentation of reasons for missingness, (2) data reports from baseline and post-intervention timepoints to identify and resolve data entry errors (e.g., scores outside of possible range), and (3) monitor current volunteer status in study including an opportunity for the assessor and/or interventionist to identify problems and solutions that may have occurred during data collection.

16.0 Health Information and Privacy Compliance

16.1	Select which of the following is applicable to your research:
	$\hfill \square$ My research does not require access to individual health information and therefore assert HIPAA does not apply.
	☑ I am requesting that all research participants sign a HIPCO approved HIPAA Disclosure Authorization to participate in the research (either the standalone form or the combined consent and HIPAA Authorization).
	$\hfill \square$ I am requesting the IRB to approve a Waiver or an alteration of research participant authorization to participate in the research.
	Appropriate Use for Research: N/A

Page 29 of 44

	Stroke Sedentary Behavior Using Telehealth (Formative Phase)
	ATE: 07.21.2023
	☐ An external IRB (e.g. Advarra) is reviewing and we are requesting use of the authorization language embedded in the template consent form in lieu of the U of M stand-alone HIPAA Authorization. Note: External IRB must be serving as the privacy board for this option.
16.2	Identify the source of Private Health Information you will be using for your research (Check all that apply)
	☑ I will use the Informatics Consulting Services (ICS) available through CTSI (also referred to as the University's Information Exchange (IE) or data shelter) to pull records for me
	oxtimes I will collect information directly from research participants.
	☐ I will use University services to access and retrieve records from the Bone Marrow Transplant (BMPT) database, also known as the HSCT (Hematopoietic Stem Cell Transplant) database.
	\square I will pull records directly from EPIC.
	\square I will retrieve record directly from axiUm / MiPACS
	\square I will receive data from the Center for Medicare/Medicaid Services
	\square I will receive a limited data set from another institution
	☐ Other. Describe: N/A
16.3	Explain how you will ensure that only records of patients who have agreed to have their information used for research will be reviewed.
	PHI data will only be collected directly from volunteers who have provided informed consent to participate in the study. Data retrieved from the Informatics Consulting Service through the CTSI for recruitment will be filtered by Informatics Consulting Service staff to include only those patients who have agreed to have their information used for research. However, providers who have a treating relationship with the patient may discuss research opportunities during a clinical encounter regardless of research opt-out status and opt-out status will not matter if a participant contacts us first.
16.4	Approximate number of records required for review: 3,700
16.5	Please describe how you will communicate with research participants during the course of this research. Check all applicable boxes
	☐ This research involves record review only. There will be no communication with research participants

VERSION DATE: 07.21.2023

- ☐ Communication with research participants will take place in the course of treatment, through MyChart, or other similar forms of communication used with patients receiving treatment.
- □ Communication with research participants will take place outside of treatment settings. If this box is selected, please describe the type of communication and how it will be received by participants.
- Throughout the course of the study, communication with research volunteers will occur via mail, telephone calls, videoconferencing, and if requested by the volunteers to minimize burden, text messages and/or emails.
- **Mail:** The study team will mail paper copies of the informed consent document, study materials (workbook, activity monitoring supplies), and study remuneration materials (ClinCard).
- **Telephone calls**: The study team will use telephone calls for the purposes of scheduling study visits, appointment reminders, study screening, and general study communications as needed.
- **Videoconferencing**: The study team will use the University of Minnesota Health Care Component Zoom account to interact with participants on their own devices to complete study assessments, interviews, and intervention sessions.
- **Text messages:** The study team will use text messages on a limited basis for the purpose of sending appointment reminders and scheduling. Text messages will only be used if the participant specifically requests method of communication.
- Emails: The study team will use email on a limited basis for the purpose of sending blank informed consent documents in preparation for the study consent meeting and sending appointment reminders. No PHI will be sent using email. Email will only be used if the participant specifically requests to receive materials and/or appointment reminders using this modality. We are requesting a waiver of the use of encrypted email to send study appointment reminders and blank informed consent documents
- 16.6 Explain how the research team has legitimate access to patients/potential participants:

The research team will not access medical records of enrolled volunteers. Private information about volunteers who are enrolled in the study will be collected by study staff directly from the volunteers themselves. Because the volunteers have enrolled in the study, signed a HIPAA authorization form at the time of informed consent and are willingly providing the information as approved by the IRB, the study team has legitimate access to these data.

Page 31 of 44 Template Revised On: 10/28/2022

DATE: 07.21.202 Location(s) of s research data (torage, sharing	and analysis of research data, including any links to pply).
oxtimes In the data s	helter of the Ir	formation Exchange (IE)
Store	oxtimes Analyze	☐ Share
	-	plant (BMT) database, also known as the HSCT nsplant) Database
\square Store	\square Analyze	☐ Share
⊠ In REDCap (ı	ecap.ahc.umn.	edu)
Store	oxtimes Analyze	Share
\square In Qualtrics	(qualtrics.umn.	edu)
\square Store	\square Analyze	☐ Share
\square In OnCore (d	oncore.umn.ed	u)
\square Store	\square Analyze	☐ Share
oxtimes In the Unive	rsity's Box Secu	ure Storage (box.umn.edu)
⊠ Store	oxtimes Analyze	Share
☐ In an AHC-IS Support Contact		ver. Provide folder path, location of server and IT
\square Store	\square Analyze	☐ Share
□⊠ In an AHC	:-IS supported o	desktop or laptop.
establish access	s to a remote H	of all devices: We are working with HST IT to IST/Citrix desktop which will be used to store, e data through REDCap and Box.
$\square \boxtimes$ Store	$\square oxtimes$ Analyze	☐ Share
☐ Other. Desc	ribe:	
Describe in det analyzed, or sh		and whether the data / specimens will be stored, nat ways.
server, desktop computer such	, laptop, exteri as an iPad or a	ed, downloaded, accessed, shared or stored using a nal drive or mobile device (including a tablet smartform (iPhone or Android devices) that you the preceding questions
☐ I will use a s	erver not previ	ously listed to collect/download research data

VERSION DATE: 07.21.2023

☐ I will use a desktop or laptop not previously listed: Research staff will use
university-owned DWELL Laboratory laptops supported by the College of
Education and Human Development IT team to analyze deidentified data using
local programs (e.g., SPSS, R, NVivo, PalTechnologies). Deidentified datasets and output from analyses will be stored on BOX.
\square I will use an external hard drive or USB drive ("flash" or "thumb" drives) not previously listed
☐I will use a mobile device such as an tablet or smartphone not previously listed

16.8 Consultants, Vendors, Third Parties.

BrightOutcome: The electronic version of the Activity Card Sort (ACS3) is completed using an online system managed by BrightOutcome (Buffalo Grove, IL, USA). The data collected using this system will only be identified using the study ID code. No direct identifiers will be entered. The ACS3 is encrypted using AES-256-CBC. Data will be exported from BrightOutcome via .csv files and stored in the University of Minnesota Box Secure folder.

PalTechnologies: Data collected using the activPAL monitors will be processed and data visualizations will be created using PalAnalysis (PalTechnologies, Glasgow, Scotland). The data collected using activPAL monitors will only be identified using the study ID code. No direct identifiers will be entered. This software is downloaded and runs locally using a university-owned computer.

- 16.9 Links to identifiable data: Numeric study codes will be assigned by the research team sequentially upon volunteer enrollment into the study. The only place where the volunteer's name and number will be linked are the linking file stored in the REDCap database. All fields on the linking file form will be marked as identifiers. The linking file form will be deleted from the REDCap database by the PI after the study is completed and the federal requirements for record retention has lapsed.
- 16.10 Sharing of Data with Research Team Members. Research team members will be granted access to the REDCap database, BrightOutcome portal, and/or shared University of Minnesota Secure Box folder based on the data that they require to complete their role in the study. Team members will only access these files and portals from a university-owned laboratory device
- 16.11 Storage of Documents: Paper documents generated as a result of this research project will be stored in a locked filing cabinet in [name] private locked office in the School of Kinesiology (located at Cooke Hall). Electronic documents generated as a result of this research project will be stored on the University of Minnesota Secure Box folder and on DWELL Laboratory devices.

Page 33 of 44 Template Revised On: 10/28/2022

VERSION DATE: 07.21.2023

16.12 Disposal of Documents: All data will be retained for a minimum of 3 years, in alignment with the NIH retention policy. After 3 years, the linking file will be destroyed as described in section 16.9. Deidentified data and audiorecordings of interviews and intervention sessions will be retained on the University of Minnesota Secure Box folder in perpetuity to allow for secondary analyses of the data and to support future laboratory staff training to the intervention protocol.

17.0 Confidentiality

- 17.1 Data Security: Data collected electronically will be stored in the University of Minnesota Box Secure Storage and REDCap. These data will be accessed using University-owned password-protected computers and access to research data stored in these systems will be provided to trained study staff who require access to data relevant to their role on the study. All data will be stored using a study ID code, and the only place where the participant's name and study ID code are linked will be in the REDCap linking form. All fields in the REDCap linking form will be marked as identifiers to prevent the export of identifiers. Paper documentation generated as a result of this study will be stored in a locked file cabinet in the locked DWELL Research Laboratory in the School of Kinesiology. Informed consent will be completed electronically and completed consent documents will be stored in a REDCap project separate from the participant's study data. A copy of the consent form will **not** be placed in the participant's medical record. Only study staff who require access to electronic or paper files will be granted access. These staff will be required to complete HIPAA, ISP, and CITI training modules on Good Clinical Practice prior to receiving access to these data. This is an NIH-funded study, and therefore all data are protected under a certificate of confidentiality.
- 17.2 Data Sharing: There are no current plans for data sharing. Upon completion of the study, a master de-identified dataset will be created and stored in the study BOX site. This dataset will include questionnaire data, raw and processed activPAL data, and transcribed interview data. Upon request for data sharing, the PI will follow procedures to establish a data use agreement that provides only the necessary data from the master de-identified dataset.

18.0 Provisions to Monitor the Data to Ensure the Safety of Participants

- 18.1 Data Integrity Monitoring. Data integrity will be monitored by the PI, who has over 10 years of experience working with people with stroke-related disability in clinical (as an occupational therapist) and research settings. The following strategies will be applied:
 - 1. The study team will notify the PI of new study enrollments and the PI will review the screening documentation form within 2 business days to confirm eligibility to proceed with the informed consent meeting.

Page 34 of 44

VERSION DATE: 07.21.2023

- 2. Procedural checklists will be reviewed for completeness following each study visit by the study staff responsible for each visit. Reasons for missing data will be documented in REDCap.
- 3. The PI will hold weekly meetings with the study team to review study enrollment, monitor volunteer progression through study procedures, review case report forms, and monitor adverse events. Meetings will be documented and meeting minutes will be stored electronically with the study files in the University of Minnesota Box Secure Storage.
- 18.2 Data Safety Monitoring. This study will be overseen by a data safety monitor external to the trial and institution who has expertise in neurorehabilitation trials. The PI will meet with the data safety monitor every 6 months to review a report that includes: participant accrual, adverse events data, and data completeness. Adverse events data will be collected at two timepoints during the study: (1) during the interview 1 session, and (2) during post-intervention assessments. Data will be collected over the telephone or Zoom using a questionnaire. Ad hoc reports of adverse events will also be collected by any study staff who become aware of an adverse event during any study interaction. Whomever first identifies the adverse event will complete an ad hoc form and notify the PI who will determine appropriate follow-up actions and reporting.

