12.0 Withdrawal of Participants

- 12.1 Withdrawal Circumstances: Participants are free to withdraw from participation in the study at any time upon request. An investigator may discontinue a participant from the study for the following reasons:
 - The PI and intervention therapist determines that they are consistently not following safety plans associated with the activities that are planned during intervention. An example of this would occur when the safety protocol that the volunteer and intervention therapist agreed to during the prior intervention session requires the participant to have their caregiver/support person present when they engage in an activity, and the participant subsequently reports that they completed the activity alone.
 - The volunteer is re-hospitalized for any medical reason during the assessment or intervention period. Depending on the circumstances of the re-hospitalization, the volunteer may be offered partial withdrawal (i.e., terminate intervention but complete the Week 8 assessments and/or study exit interview).
- 12.2 Withdrawal Procedures: Volunteers who notify study staff verbally and/or in writing that they wish to withdraw from the study will be offered the choice of full withdrawal or partial withdrawal. Full withdrawal constitutes no further intervention sessions or data collection. Data that were collected prior to the date and time of the volunteer's notification to study staff will be maintained under their study ID code for analysis. Partial withdrawal constitutes no further intervention sessions and agreement to be contacted for subsequent assessment and interview timepoints. The staff member whom the volunteer notifies will document the conversation in the study record, including whether the volunteer has elected full or partial withdrawal, and (if the staff member notified is not the PI) will notify the PI. If the volunteer notifies the study in writing that they wish for their previously collected data to be destroyed, the study team will destroy all previously collected data (including REDCap record, activity monitoring files, and audiorecorded interviews and intervention sessions)
- 12.3 Termination Procedures: If the study is suspended or terminated, the study team will cease all research activities. The study team will immediately take the following steps to notify volunteers based on their status in the study:

Page 25 of 44

VERSION DATE: 07.21.2023

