- Currently wearing activPAL Monitor during Week 1 or Week 8
 assessments: The study team will contact volunteers and request that
 they immediately remove the activPAL monitor and return it to the study
 team using the pre-paid envelope that is provided with each device.
- Currently completing intervention sessions: The study team will contact the volunteers to notify them that the study has been terminated and that all scheduled intervention sessions have been cancelled.
- Scheduled for upcoming assessment sessions (Week 1, Week 8) or interviews (Interview 1, Interview 2): The study team will contact the volunteers to notify them that the study has been terminated and that all scheduled assessment sessions and interviews have been cancelled.
- Scheduled for upcoming informed consent meeting: The study team will
 contact the interested volunteer to notify them that the study has been
 terminated and that enrollment has been closed to new volunteers.
- All data collected prior to study termination will be maintained in its coded form to allow data analysis. Identifiers will be destroyed and data will be maintained in its deidentified form after it is confirmed that the study is permanently closed to new enrollment.

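### No adverse-event enquiry is planned at withdrawal or discontinuation, so some leavers are never systematically asked about events that count towards the safety benchmark

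*Combined protocol and SAP*

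**What the plan says.** Section 18.2 sets the schedule: "Adverse events data will be collected at two timepoints during the study: (1) during the interview 1 session, and (2) during post-intervention assessments". The method is simple: "Data will be collected over the telephone or Zoom using a questionnaire". A second, unscheduled route follows: "Ad hoc reports of adverse events will also be collected by any study staff who become aware of an adverse event during any study interaction". Section 18.1 adds weekly team meetings at which adverse events are monitored.

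Section 12.2 gives anyone who asks to withdraw two options. On the first it says: "Full withdrawal constitutes no further intervention sessions or data collection". The second, partial withdrawal, stops the sessions but leaves the person contactable for later assessments and interviews. Data gathered before the withdrawal notice are normally kept.

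Section 12.1 lists two grounds on which an investigator may discontinue someone. One is: "The volunteer is re-hospitalized for any medical reason during the assessment or intervention period". In that case partial withdrawal is something the person may be offered, depending on circumstances. The other ground is persistent failure to keep to agreed safety plans, and no follow-up is described for it.

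The safety outcome in section 3.2 covers treatment-related events in weeks 2 to 7, both serious and non-serious, and a fall without injury is its example of the latter. Section 15.3 sets the benchmark at no more than 1 adverse event. Section 10.1 aims for 5 to 10 completers and allows up to 15 to be consented.

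**The concern.** Both scheduled enquiries are tied to later study visits, and nothing is scheduled at the moment of leaving. For a full withdrawer, or a person discontinued without an offer of partial withdrawal, the plan then relies on an event having come to staff attention in some other way.

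That matters because safe remote delivery is part of Aim 1, safety is a secondary outcome, and the benchmark is very low. At that threshold an unrecorded minor event can be the difference between missing and meeting it. There is no second source to recover such events: section 16.6 says the team will not look at the medical records of enrolled volunteers, and section 19.2 says all data come from participants.

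**Working it through.** **1. The plan's own contact counts (section 15.2).** Each person has 12 sessions and 2 interviews.
- 5 × 12 = 60 and 10 × 12 = 120 sessions.
- 5 × 2 = 10 and 10 × 2 = 20 interviews.

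Both ranges match the protocol. With two adverse-event questionnaires per person, the scheduled enquiries also number 10 to 20, against 60 to 120 sessions at which an event might be mentioned.

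**2. What each type of leaver is asked.** Interview 1 falls within 14 days after session 5 (section 5.2). At two sessions a week, that is after session 5 at the earliest and about session 5 + 4 = 9 at the latest.

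| Exit | Interview 1 enquiry | Week 8 enquiry | Period not asked about |
|---|---|---|---|
| Full withdrawal before Interview 1 | No | No | Session 1 to exit |
| Full withdrawal after Interview 1 | Yes | No | Interview 1 to exit |
| Partial withdrawal, later visits attended | Yes | Yes | None |
| Re-hospitalized and discontinued | If already held | Only if partial withdrawal is offered and the week 8 assessments are completed | Depends on the offer |
| Discontinued over safety plans | If already held | Not described | Last enquiry to exit |

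**3. How many people.** If all 15 are consented and 10 complete, there are 15 − 10 = 5 leavers. Full ascertainment would be 15 × 2 = 30 enquiries. The number held would be:
- 20 + 5 × 0 = 20 if all five leave fully before Interview 1;
- 20 + 5 × 1 = 25 if each has one enquiry;
- 20 + 5 × 2 = 30 if all choose partial withdrawal and attend both.

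**4. Sensitivity of the benchmark.** Section 15.3 does not say whether the limit applies to the whole study or to each person; I take it as study-wide. A true count of 2 misses the benchmark, and one unrecorded event turns it into 1, which meets it. A true count of 3 needs two unrecorded events.

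**5. Illustration with assumed risks, none of them from the documents.** Take 10 completers, each with a 10% chance of an event and all events recorded. Add 5 leavers with event risk q, of which a fraction c is recorded. Assume at most one event per person and independence. Then

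P(recorded count ≤ 1) = (A0 + A1)·B0 + A0·B1,

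where
- A0 = 0.9^10 = 0.3487
- A1 = 10 × 0.1 × 0.9^9 = 0.3874
- B0 = (1 − qc)^5
- B1 = 5qc(1 − qc)^4

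For q = 0.30 and c = 1: B0 = 0.1681 and B1 = 0.3602, so 0.7361 × 0.1681 + 0.3487 × 0.3602 = 0.25.

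| Leaver risk q | All recorded | Half recorded | None recorded |
|---|---|---|---|
| 10% | 0.55 | 0.64 | 0.74 |
| 30% | 0.25 | 0.46 | 0.74 |
| 50% | 0.08 | 0.31 | 0.74 |

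The last column is a bound, not a forecast, because the ad hoc route will record some events.

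**The case against.** The best defence is that the questionnaire is not the only route. Any staff member who learns of an event at any interaction completes a form and tells the principal investigator. Staff are trained in identifying and reporting events (section 25.1), and adverse events are reviewed weekly. Participants are seen twice a week, and from session 3 onward the therapist goes over how the planned activity went (Table 2), which is when a related fall would tend to surface. Partial withdrawal is offered to everyone who asks to leave. A re-hospitalization or safety-plan breach must already be known to staff before it can lead to discontinuation. The monitor's report also covers data completeness, so absent questionnaires need not go unseen.

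Most of this stands. It rules out a stronger reading that a reader might infer: that leavers do not attend the two enquiry visits, and that the safety count therefore comes mainly from people who stay well. Partial withdrawal keeps those visits open, earlier reports are normally kept, and the events behind a section 12.1 exit are likely to be recorded ad hoc.

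What the defence does not supply is a question asked of every leaver. The ad hoc route works only when staff become aware of an event, and Table 2 lists no adverse-event enquiry among the session contents. A harmless fall since the last session may not be volunteered by someone calling to stop. Knowing of an admission for any medical reason does not settle whether it was treatment-related, which is what section 3.2 counts. Section 12.2 requires the withdrawal conversation to be documented, but does not require an event to be asked about.

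**Conclusion.** The gap is real but limited. Systematic enquiry is missing for full withdrawers and for people discontinued without follow-up. It covers the time since session 1 if they leave before Interview 1, and the time from Interview 1 to exit if they leave later. With 10 completers among 15 consented, up to 5 people could be affected. One or two missed events could change whether the benchmark is met, assuming it applies to the whole study. The documents do not show how many events would be missed, and the probabilities above only illustrate sensitivity.

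Three further inferences are not supported:
- Pairing the maximum of 15 consented with only 5 completers would give more leavers, but section 10.1 offers 15 as an allowance for withdrawals, not as an expected loss of that size.
- Study termination also cancels visits, but it affects everyone still enrolled and does not select people by how well they are.
- Destruction of data on written request (section 12.2), set beside the three-year retention rule (section 16.12), is a separate question of participants' data rights. Section 12.2 can be read as a specific exception, and the consent pages are not available to settle it.

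This is worth correcting because safety is a benchmarked secondary outcome and the remedy is small. It does not undermine a descriptive formative study whose primary outcome is satisfaction.

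**What to change.** In sections 12.1 and 12.2, have the staff member who handles the withdrawal or discontinuation give the existing section 18.2 questionnaire at that contact, if the person agrees, covering the time since the last enquiry (or since session 1 if there was none). Record whether an event prompted the exit. State that these answers are kept as study data, since section 12.2 currently refers only to data collected before the notice.

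In section 15.3, count events in everyone who started session 1, and report how many of them had the Interview 1, exit and week 8 enquiries, so that a low count can be read against how fully people were asked.

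The cost is a few minutes per leaver at a contact that already takes place, plus a short amendment with matching consent wording. Some leavers will decline, and the reported count may be less favourable.
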